6.4 DEMOGRAPHIC AND BASELINE CHARACRISTICS

Summary statistics (number of subjects, mean, standard deviation, median, minimum and maximum) will be provided for numerical variable age.

Frequency summary (number and percentage of subjects) will be provided for categorical variables including sex, race, ethnicity and Fitzpatrick skin type classification.

6.5 SAFETY ANALYSIS

All subjects who have IP applied at least once will be included in the safety analysis. All AEs reported during the AE reporting period will be listed by subject number.

The number and percentage of subjects experiencing treatment-emergent adverse events will be presented by body system and preferred term. Treatment-emergent adverse events are those with a start date and time on or after the date and time of first use of investigational product, or the AEs started before the first use of investigational product and worsened after it. The latest version of the Medical Dictionary for Regulatory Activities (MedDRA) will be used as the adverse event classification system.

Number and percentage of subjects with serious adverse events will be summarized by MedDRA system organ class and preferred term.

Number and percentage of subjects with treatment-related adverse events will be summarized by MedDRA system organ class and preferred term. Treatment-related AEs are events evaluated by the investigator as possible, probable or very likely related to

Protocol CCSTOH001689
Statistical Analysis Plan

investigational product. AEs with unknown relationship to treatment will be considered as treatment-related.

APPENDICES

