8.3.3. Exploratory Endpoints

8.4. AE ANALYSIS

All subjects who have IP applied at least once will be included in the safety analysis. All AEs reported during the AE reporting period will be listed by subject number. The number of subjects experiencing AEs will be presented by body system, preferred term, and treatment (if assessed as related to a particular IP). The latest version of the Medical Dictionary for Regulatory Activities (MedDRA) will be used as the adverse event classification system.

Version & Date: Amendment 3: Final Version 4.0, 28 Aug 2019

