4.3 Safety Assessments and Endpoints

Safety assessments consist of Adverse Events.

- Number and percentage of subjects with treatment-emergent adverse event
- Number and percentage of subjects with treatment-related adverse event
- Number and percentage of subjects with serious adverse event

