APPENDIX 1: SUMMARY TABLES AND FIGURES

The following tables and figures are planned for subsections in Sections 14 of the Clinical Study Report. The numbering and titles of tables and figures in this document serves as guidance; the exact numbers and titles may be modified as appropriate.

Section / Table No	Title	Population / Analysis Sets
--------------------	-------	----------------------------

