14.3 Safety

Section / Table No	Title	Population / Analysis Sets
Table 14.3.1	Subjects with Treatment-Emergent Adverse Events by System Organ Class and Preferred Term	Safety Analysis Set
Table 14.3.2	Subjects with Treatment-related Adverse Events by System Organ Class and Preferred Term	Safety Analysis Set

Protocol CCSTOH001689
Statistical Analysis Plan

Table 14.3.3	Subjects with Serious Adverse Events by System Organ Class and Preferred Term	Safety Analysis Set
--------------	---	---------------------

Protocol CCSTOH001689
Statistical Analysis Plan

FIGURES:

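### SAP 6.5 summarises treatment-related AEs without the treatment breakdown that Protocol 8.4 sets for AEs related to a particular IP, so the summary does not identify the dressing (minor)

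*SAP*

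**What the plan says.** Protocol 8.4 says that the number of subjects with AEs is to be "presented by body system, preferred term, and treatment (if assessed as related to a particular IP"). Treatment is thus a third dimension, but a conditional one.

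SAP 6.5 has separate summaries for treatment-emergent, serious and treatment-related AEs, and none names treatment. For treatment-related AEs: "Number and percentage of subjects with treatment-related adverse events will be summarized by MedDRA system organ class and preferred term". For treatment-emergent AEs: "The number and percentage of subjects experiencing treatment-emergent adverse events will be presented by body system and preferred term". SAP 4.3 lists the matching endpoint per subject only: "Number and percentage of subjects with treatment-related adverse event". SAP 6.5 also widens the related category: "AEs with unknown relationship to treatment will be considered as treatment-related".

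In SAP Appendix 1, Table 14.3.2 is titled "Subjects with Treatment-related Adverse Events by System Organ Class and Preferred Term", with the caveat that "the exact numbers and titles may be modified as appropriate". For individual events, SAP 6.5 says: "All AEs reported during the AE reporting period will be listed by subject number".

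On the design, Protocol 6.6 randomizes one study treatment to each of the eight wound sites. The Protocol synopsis puts IPs on seven of them and leaves the eighth uncovered.

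**The concern.** In a parallel-group trial a safety table gets its treatment columns from the arms, even if the SAP text does not mention them. Here every subject is exposed to all seven IPs and also has an untreated site. A count of subjects by system organ class and preferred term is therefore a count over everyone, whichever dressing was involved.

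The protocol anticipated this by asking for treatment where an event is judged related to a particular IP. The SAP, which governs the tables, does not carry that request forward and does not explain why. The trial exists to compare dressings. At stake is whether its related-AE summary can show events gathering on one prototype or benchmark rather than being spread across several.

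**Working it through.** The plan gives no figure to reproduce here. The check is a comparison of texts plus a count of columns and denominators.

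**Step 1: compare the rules for related AEs.**

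| Source | Dimensions named | Treatment named? |
|---|---|---|
| Protocol 8.4 | body system, preferred term, treatment | yes, if related to a particular IP |
| Protocol 10.3.3, tabulation of AEs | AE type (for example related or not related to product or study) | no |
| SAP 4.3 | subjects with a related event | no |
| SAP 6.5 | system organ class, preferred term | no |
| SAP Table 14.3.2 (title) | system organ class, preferred term | no |

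SAP 6.5 otherwise follows Protocol 8.4 closely: the safety set, the listing order and the MedDRA statement match. The difference lies in how events are tabulated.

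**Step 2: could treatment be implied?** Where the SAP methods text wants results by treatment, it says so. In SAP 6.3 the Kaplan-Meier estimates are made separately for each treatment, and self-assessment questions 2 and 4 are summarised for each treatment. SAP 6.5 has no such wording, and no readable SAP text supplies it elsewhere.

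**Step 3: what the tables would contain.**
- SAP as written: 1 column, with all subjects who had any IP applied as denominator.
- Protocol 8.4 applied to this design: 7 IP columns, each with the subjects who had that IP applied as denominator. Related events that cannot be assigned to one IP also need a place, including those of unknown relationship. That makes 7 + 1 = 8 columns.

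**Step 4: how much a treatment column could show.** The plan enrols up to 40 subjects and targets at least 30 completers, so each IP column would have about 30 to 40 subjects. The documents give no expected AE rate, so only the resolution can be stated. With zero events among n subjects, the upper limit of the exact two-sided 95% interval is 1 − 0.025^(1/n):
- n = 40: 1 − 0.025^(1/40) = 8.8%
- n = 30: 1 − 0.025^(1/30) = 11.6%

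An empty column would therefore still be compatible with a true rate of roughly 9% to 12%. The columns would describe where events fell and would not support tests between dressings.

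**Step 5: is the attribution collected?** Protocol 10.3.2.4 rates causality against participation in the study, not against a named dressing. SAP 6.5 defines treatment-related by relation to investigational product, without saying which one. Protocol 10.3.3 asks for IP information on SAE reports only where applicable. Protocol section 12 lists adverse events as captured in the EDC system but does not give the fields. No readable text specifies a wound-site or per-IP field for AEs in general, although Protocol 8.4 presumes that relatedness to a particular IP can be assessed.

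**The case against.** The strongest reply is that the SAP is silent rather than contrary. It nowhere says that Protocol 8.4 is superseded, and it did not simply delete a word: it replaced one tabulation sentence with three summaries. The treatment-emergent summary is largely outside the protocol's condition, so the real evidence is the related-AE sentence alone. This is fair and narrows the point. That sentence still states its dimensions and leaves treatment out.

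Second, table titles prove little. They are guidance, and the titles of Tables 14.2.9 and 14.2.10 also omit treatment although SAP 6.3 makes those summaries by treatment. This stands, so the point rests on the SAP 6.5 text.

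Third, the protocol is not uniform, because its own tabulation in 10.3.3 names no treatment. This also stands. It softens the departure but does not remove the explicit rule in 8.4.

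Fourth, a reader might infer that the report could not attribute events to a dressing at all. The documents do not support that. Listing 16.2.7.1 (adverse events) and Listing 16.1.7 (randomization scheme and codes) are both planned. Ordering by subject number does not mean that the site or IP is absent, and with at most 40 subjects the events can be read one by one if the site is recorded. What remains is that a listing is not the count by treatment that Protocol 8.4 describes.

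Fifth, a reader might infer that dressing-related wound infections would be hidden. Protocol 6.5.2 does have signs of infection documented as an AE, but the treatment breakdown applies only if the event is judged related to a particular IP. An infection at a laser wound could be attributed to the procedure instead.

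**Conclusion.** The point holds in limited form. SAP 6.5 departs, without explanation, from the conditional by-treatment presentation in Protocol 8.4. In this within-subject design the result is one pooled related-AE column that does not identify the dressing.

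It is minor. Only descriptive safety reporting is affected, and no efficacy result depends on it. Erythema, edema, pain and itch scores are already compared between treatments under SAP 6.3, and Protocol 10.3.2.1 keeps expected mild reactions out of the AE data.

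Two wider readings are not supported. Protocol 8.4 does not require all AEs by treatment. Nor does it call for a count at the uncovered site, which is not an IP; such a table would be an addition and does not follow from this discrepancy.

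The conclusion assumes that no blacked-out SAP text restores the treatment dimension. How easily the fix can be carried out depends on whether the AE record holds the wound site or related IP, which the readable text does not settle.

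**What to change.** In SAP 6.5 and the layout of Table 14.3.2:
- Add treatment as a dimension for AEs assessed as related to a particular IP, using the subjects who had that IP applied as denominator.
- Present these counts descriptively, without tests.
- Add one column for related AEs not tied to a single IP, including those of unknown relationship.

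In Listing 16.2.7.1, show the wound site or related IP. Confirm that the AE record captures it, since the causality scale alone does not. If the sponsor prefers the pooled table, the SAP should state and justify the departure from Protocol 8.4.

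The cost is a short addition to SAP 6.5, a somewhat wider table with small counts, and possibly one added AE data field. No new visits are needed. If relatedness to a particular IP is not being recorded, the text change alone cannot produce the table, so this should be checked first.

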10.3.2.4. Causality Assessment

An AE (serious or non-serious) is considered "study-related" if the causality assessment is possible, probable, or very likely. The Study Physician determines the causality by using the following definitions:

- Not related an AE that is not related to the participation in the study.
- **Doubtful** an AE for which an alternate explanation is more likely (e.g. concomitant drug), or the relationship in time suggests that a causal relationship is unlikely.
- Possible an AE that might be a result of participation in the study. An alternative explanation is
 inconclusive and the relationship in time is reasonable so a causal relationship cannot be
 excluded.
- **Probable** an AE that might be a result of participation in the study. The relationship in time is suggestive (e.g. confirmed by the challenge). An alternative explanation is less likely.
- **Very Likely** an AE that is listed as a possible adverse reaction and cannot be reasonably explained by an alternative explanation. The relationship in time is very suggestive (e.g. confirmed by dechallenge and rechallenge).

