10.3.3. Procedures for Reporting AEs

All AEs will be reported from the time a signed and dated ICD is obtained until completion of the subject's last study procedure or visit (or termination if the subject terminates early from the study for any reason).

AEs that occur within 30 calendar days after completion of the study will only be reported to the Sponsor if they are serious (i.e. SAEs). SAEs are reportable beyond this period if the event is considered study-related. The Sponsor will evaluate any safety information that is spontaneously reported by the PI/Site beyond this time frame.

Subjects are encouraged to report AEs spontaneously and in response to questioning during the visit (e.g. if they have had any side effects/issues or changes in their health since their last appointment). For each AE reported by the subject or observed by the Site team, the Site team member should notify the PI or designee, who will collect information about the event.

All AEs, regardless of seriousness, severity, or presumed relationship to study procedures, must be recorded using medical terminology. Whenever possible, diagnoses should be given when signs and symptoms are due to a common etiology (e.g., cough, runny nose, sneezing, sore throat, and head

Different Adhesive Bandages Protocol Number: CCSTOH001689

Version & Date: Amendment 3: Final Version 4.0, 28 Aug 2019

congestion should be reported as "upper respiratory infection"). The Study Physician must record or confirm their opinion concerning the seriousness, severity, and relationship of the AE to the study. All measures required for AE management must be recorded and reported according to Sponsor instructions.

These events must then be entered into the EDC system within 3 business days of the Site's awareness.

Tabulation of AEs

AEs will be reported in a table detailing the different AE types highlighted in this protocol:

- Pre-Treatment AEs (PTAEs)
- Expected AEs
- AEs related to the product(s)/study
- AEs not related to the product(s)/study
- SAEs related to the product(s)/study
- SAEs not related to the product(s)/study

Additional Reporting Procedures

The PI or designee must also report AEs to the appropriate IRB/IEC unless otherwise required and documented by the IRB/IEC.

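### Causality is rated against study participation but reported as relation to the investigational product, so procedure reactions may be counted as IP-related unless a separate IP rating is collected

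*SAP*

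**What the plan says.** Protocol 10.3.2.4 sets out a five-level causality scale. Its lowest level is "an AE that is not related to the participation in the study", and both the possible and probable levels begin with "an AE that might be a result of participation in the study". An AE is labelled study-related "if the causality assessment is possible, probable, or very likely".

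Protocol 10.3.3 states what is put on record: "The Study Physician must record or confirm their opinion concerning the seriousness, severity, and relationship of the AE to the study". Its list of AE types for tabulation has a combined category, "AEs related to the product(s)/study".

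The SAP lists subjects with treatment-related AEs as one of three safety endpoints (4.3) and reports them in Table 14.3.2. SAP 6.5 defines the term: "Treatment-related AEs are events evaluated by the investigator as possible, probable or very likely related to" investigational product. It adds: "AEs with unknown relationship to treatment will be considered as treatment-related".

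Two places in the protocol point to a judgement about the product itself. Protocol 8.4 plans to present AEs by body system, "preferred term, and treatment (if assessed as related to a particular IP"). Protocol 4.4, on concomitant medication, names IP-related and study-related AEs as two different things.

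**The concern.** The SAP uses the same grade names as the protocol but changes what they are measured against. In many trials the difference would be small, because taking part mostly means taking the product. Here, every subject also receives eight laser wounds, anaesthetic cream at each site, semi-permanent ink beside the wounds and a cleanser from screening onward. None of these is an IP; Protocol Table 1 lists the cleanser separately as the auxiliary product.

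If the protocol's rating is the one passed to the SAP, the treatment-related table answers whether the trial caused the event. Its title and definition say that it answers whether an IP did. Events caused by the wounding model would then be mixed with events caused by the bandages, and a real product reaction would be harder to see. Protocol 6.5.2 requires excessive redness, pain, swelling or signs of infection at a wound to be documented as an AE. For events of that kind, separating a laser cause from a bandage cause matters most.

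**Working it through.** The documents state no figure on this point, so the check is mainly a comparison of text.

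1. **What is rated.** Three of the five levels in Protocol 10.3.2.4 (not related, possible, probable) are worded against participation in the study. The other two (doubtful, very likely) name neither participation nor a product. The collective label for the top three levels is study-related.

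2. **What is recorded.** Protocol 10.3.3 asks for the relationship of the AE to the study. Protocol 12 lists adverse events as data captured in the EDC system but gives no fields. Neither document describes an IP-level causality item.

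3. **What is reported.** SAP 6.5 takes possible, probable and very likely as relation to the IP, and sends unknown relationships to the same side.

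4. **What follows if only the defined rating exists.** A procedure reaction rated possible or probable is either carried across under its grade, or treated as having no known relation to the IP. Both routes lead into Table 14.3.2.

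5. **What follows if an IP rating is collected and used.** SAP 6.5 can then be applied as worded, and the misclassification does not arise. Protocol 8.4 and 4.4 suggest that such a judgement was intended. The gap is that it has no scale and no data item, and that SAP 6.5 makes no link to it. SAP 6.5 also omits the presentation by treatment that 8.4 announces.

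6. **Which events are exposed.** Protocol 10.3.2.1 accepts AEs arising from study procedures. It excludes expected mild reactions to laser wounding, normal healing and IP removal, unless they become moderate or severe. So for the laser, moderate or severe reactions are the main exposure. The exemption does not name the cream, ink or cleanser.

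7. **Two cases that show the difference.**
   - One of the eight sites stays uncovered (Protocol 7.2.5.2). A laser reaction there can be study-related although no bandage touched that site. If procedure reactions were equally likely at every site (an assumption), 1/8 = 12.5% of them would arise there.
   - Cream and laser come before the first IP application on Day 0 (Protocol 7.2.4 and 7.2.5). SAP 6.5 does not restrict treatment-related AEs to treatment-emergent ones. A study-related reaction that began before any IP is therefore not excluded by the text.

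8. **Scale of one error.** With the planned maximum of 40 subjects, one subject wrongly counted shifts the percentage by 1/40 = 2.5 points. With 30 subjects it is 1/30 = 3.3 points. How many subjects would be affected cannot be derived from the documents.

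**The case against.** The strongest reply is that the plan already foresees an IP judgement. Protocol 8.4 and 4.4 refer to one, SAP 6.5 says that the investigator evaluates relation to the IP, and the AE form, which is not in these documents, may well have a field for it. This stands as a limit on the point. A reader might infer that procedure reactions will certainly be reported as bandage-related. The documents do not support that; they show only that nothing written prevents it. Table 14.3.2 is also by system organ class and preferred term, so it would not assign an event to any one bandage.

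There are further safeguards. Expected mild laser, healing and IP-removal reactions are not AEs. Protocol 10.3.3 gives pre-treatment and expected AEs their own categories, and the SAP plans full AE listings. These narrow the exposure. However, the SAP's list of safety tables has only treatment-emergent, treatment-related and serious AEs, so the separate protocol categories do not protect Table 14.3.2.

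Counting unknown as related is a usual conservative convention. It is sound for a missing IP rating. The difficulty arises only if no IP rating was ever requested.

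Two other inferences fail:
- The protocol names the Study Physician as assessor and the SAP names the investigator. This is not a conflict, because the protocol synopsis lists the Study Physician as a sub-investigator.
- A procedure reaction need not be graded very likely. That level refers to a listed adverse reaction and to dechallenge and rechallenge, not to participation. The point rests on the possible and probable levels.

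**Conclusion.** The mismatch is real and should be corrected. The protocol defines and records causality against the study, the SAP reports the same grades as relation to the IP, and the IP-level judgement that would connect them is mentioned but not specified. The consequence is conditional: procedure or auxiliary-product reactions may be counted as IP-related if no separate IP rating is collected and used.

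The size cannot be given as an overall percentage, because the documents contain no AE rates; any figure for the overstatement would rest on invented counts. What can be said is that one of three stated safety endpoints is affected, at 2.5 percentage points per misclassified subject when 40 are analysed. The summary is descriptive, with no test attached, in a proof-of-principle study. The primary healing endpoint is not touched.

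**What to change.** - **Protocol 10.3.2.4:** rate each AE twice, once for relation to the IP (with the site number or treatment code if the event is local) and once for relation to study procedures or the auxiliary product. Align the wording in 10.3.3 so that both ratings are recorded and the combined product/study category is split.
- **SAP 6.5:** base treatment-related, and therefore Table 14.3.2, on the IP rating only. Apply the rule that unknown counts as related only to a missing IP rating. Report procedure-related AEs on a separate line.

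The cost is one extra rating per AE, with a field to hold it, and short wording changes in both documents. No visits or staff are added. If the AE form already collects an IP rating, a sentence in each document naming it and linking it to Table 14.3.2 would settle the main gap; the unknown rule and the separate procedure line would still need to be written.
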